#### **6.10 Initial Population/Final Population**

An Initial Population confirming the amount of microorganism present will be performed prior to testing, and plated in duplicate for each challenge suspension. A Final Population will be performed to confirm the amount of microorganism present at the completion of the assay.

#### **6.11 Incubation**

The inoculated plates will be incubated at 30 °C ± 2 °C for approximately 72 hours ± 4 hours. Plates may be refrigerated for up to 48 hours after incubation prior to counting.

### **7.0 CALCULATIONS AND DATA HANDLING**

Colonies will be counted on plates that have between 25 and 250 colonies per plate. If no plates provide counts in that range, counts from those plates closest to that range will be used for analysis.

The microbial population recovered from each replicate of Test A, Test B, Test C, and Test D will be calculated as follows:

$$\text{Log}_{10} \text{ Average Population} = \log_{10} (C_i \times 10^{-D})$$

Where:

$C_i$  = Average of the plates counted

$D$  = Dilution Factor of the plates counted (for example, the dilution

Neutralization is considered adequate if all recovery populations are not statistically different from the Initial Population (with the exception of Test D). See table below for summary.

Neutralization Test/Phase	Required Results for Acceptance
Test Organism Viability/Initial Population – Test C (IP)	30 minute sample cannot be statistically different from the within 1 minute sample, or the evaluation fails.
Test Material Control/Product Efficacy – Test D (Phase I)	Must be statistically different than Test C at the within 1 minute and 30 minutes samples.
Neutralizer Toxicity Evaluation – Test B (Phase II)	Cannot be statistically different at the within 1 minute or 30 minute samples.
Diluent/Recovery Broth Toxicity Evaluation – Test B (Phase III)	
Neutralization Effectiveness Evaluation – Test A (Phase IV)	

All values will be compared against the IP. The 30 minute evaluations of any test are used as a time representative to the longest possible wait time of a sample prior to being plated. A comparison will be performed against the FP to ensure the challenge suspension populations were consistent through testing.

The results and all source documents of the neutralization evaluation will be presented as an addenda in the Final Report.

## 8.0 STATISTICS

The statistical analysis for the neutralization will be performed by the Testing Facility. After calculating the  $\log_{10}$  populations recovered from Tests D, B, and A, these will be statistically compared to the Initial Population (Control) using a One-Way Analysis of Variance (ANOVA) with Dunnett Multiple Comparisons with the Control. All statistical calculations will be performed using the 0.05 level of significance for Type I ( $\alpha$ ) error.

Prior to comparing Phases to the Initial Population (Control), the 30-minute evaluation of the Initial Population should be shown to be statistically equivalent to the “time-zero” Initial Population of the microorganism. Hypotheses are:

$H_0$  : Initial Population = Test Phase, or

$H_A$  : Initial Population  $\neq$  Test Phase.

If  $p \leq 0.05$  for each comparison to the control,  $H_0$  will be rejected and the Test Phase will be considered to be significantly different from the Initial Population. There is potential for low variance of the data, which would result in rejecting  $H_0$ . The difference between the Initial Population and the Test Phase will also be used to confirm significant differences. If the difference is greater than or equal to 0.20, the two tests will be determined to be significantly different. Differences less than 0.20 between the two tests will be determined to be not different.

[figure not shown]
The Product Efficacy Evaluation is effective if the antimicrobial test product produces a significant reduction in the population of the microorganism.

The Neutralizing/Recovery Medium Inhibition Evaluations are considered non-inhibitory if all recovered populations are not statistically different from the Initial Population of the microorganism.

The Diluent Broth Inhibition Evaluation is considered non-inhibitory if all recovered populations are not statistically different from the Initial Population of the microorganism.

Signature Page for 1610457-103 01 MPS-16IPVFT05 Amendment #1 04 19 17

Signature Page for 1610457-103 01 MPS-16IPVFT05 Amendment #1 04 19 17 - System V

AE	Adverse Event
ATE	Average Treatment Effect
BD	Becton Dickinson and Company
CI	Confidence Interval
Conf Int	Confidence Interval
IP	Investigational Product
ITT	Intent To Treat
LSMean	Least Squares Mean
mITT	Modified Intent To Treat
NC	Negative Control
SD	Standard Deviation

2 Executive Summary

For average treatment effect / responder rate, the per-protocol data may be different from the modified intent to treat (mITT) data and analysis will be made separately based on both the per-protocol data and the modified intent to treat (mITT) data if two data sets are different. Summary statements will be made for each analysis to show if there are statistically significant differences found, or if Efficacy Standards are met for different comparisons. Links to tables showing analysis results will be provided.

3 Overall Study Description

3.1 Study Background

Pilot clinical studies have been completed by BD in healthy volunteers to assess the safety and efficacy of topical application at various concentrations of octenidine dihydrochloride in isopropyl alcohol as summarized in the Investigator's Brochure (IB). No drug-related adverse events (AEs) have been observed. Additionally, a clinical study was conducted to measure the systemic absorption of octenidine after topical administration of octenidine dihydrochloride in isopropyl alcohol under simulated maximal clinical usage to intact and abraded skin in healthy volunteers. No measurable octenidine in plasma was observed (lower limit of quantification was 1 ng/mL).

3.2 Objectives

The primary objective of this study is to compare the immediate antimicrobial properties of octenidine dihydrochloride [OCT] in isopropyl alcohol - clear in a single-use applicator and octenidine dihydrochloride [OCT] in isopropyl alcohol - tinted in a single-use applicator to a Negative Control and an FDA NDA-approved Active Control. Single use applicators filled with 0.9% saline will serve as the Negative Control and Chloraprep® - Hi-Lite Orange® applicator will serve as the Active Control. In agreement with the Food and Drug Administration Tentative Final Monograph (TFM) for Effectiveness Testing of a Patient Preoperative Skin Preparation, a log₁₀ reduction study (i.e., average treatment effect) will be used to determine antimicrobial efficacy based on the statistical analyses outlined in published letters from the FDA on January 19, 2017.

The secondary objective is to determine the persistent antimicrobial activity of the two Investigative Products, Active Control and Negative Control by responder rate. Log₁₀ bacterial counts at 6 hours for each treatment site will be converted to a binary (yes or no) success measure with success defined as having skin flora counts that are less than or equal to the baseline skin flora counts.

3.3 Study Design

This is a single-center and randomized design where each subject receives two different treatments out of 4 treatments, one on the left side of the body and one on the right side. This means there are 6 possible combinations of treatments (assuming A, B and C are either Investigational Product #1, Investigational Product #2 or Active Control, D is the Negative Control): A & B, A & C, A & D, B & C, B & D, and C & D.

A minimum of 72 evaluable subjects will be required to achieve a total of at least 144 test sites for groin and abdominal regions. To achieve 36 evaluable test sites from Investigational Product 1, Investigational Product 2, Active Control and Negative Control arms for groin and abdominal regions, of the minimum 72 evaluable subjects:

- 12 subjects will receive treatments from both A and B.
- 12 subjects will receive treatments from both A and C.
- 12 subjects will receive treatments from both A and D.
- 12 subjects will receive treatments from both B and C.
- 12 subjects will receive treatments from both B and D.
- 12 subjects will receive treatments from both C and D.

The two investigational products and the active control will be randomly assigned codes of A, B or C. However, due to visual differences between each of the test materials, the products cannot be blinded to all study staff. In order to guard against any bias of the study outcome, technicians who participate in product application or sample collection from subjects during treatment day procedures will not participate in the processing of samples. The technicians processing samples and/or counting the resultant plates will be blinded to the study randomization during the data gathering processes. Plate counts will be reviewed and recorded by separate BSLI staff prior to being entered into a data spreadsheet where product information (unblinding) would occur.

Subjects will be sampled for treatment day baseline microbial populations on randomly assigned sites of the abdominal and inguinal areas on both sides. Subjects will have samples collected at baseline, 30 seconds (± 5 seconds), 10 minutes (± 30 seconds) and at 6 hours (± 30 minutes) post-treatment application on both abdomen and inguinal sites. All sampling times will be calculated from the completion of the dry time of each product following application.

There is a neutralization test before the main treatment study. This test is to assure that the neutralizers used in the recovery medium quench the antimicrobial activity of the three test materials (The Investigational Products and Active Control), and that the neutralizers are not toxic to the bacteria. Note: this statistical analysis plan is only for the Main Treatment study and does not include the analysis for the Neutralization study. The analysis for the Neutralization study will be conducted by the clinical site and included in the final clinical report.

The group treatments and number of treatment sites for each group for the main treatment study are shown in Table 1.

Table 1: Group treatments and number of treatment sites for the main treatment part

Product Code	Arm	Treatment	Number of evaluable treatment sites per anatomical site
A, B or C	Investigational Product #1 (IP1)	Octenidine Dihydrochloride in Isopropyl Alcohol in a single-use applicator - clear	36
A, B or C	Investigational Product #2 (IP2)	Octenidine Dihydrochloride in Isopropyl Alcohol in a single-use applicator -tinted	36
A, B or C	Active Control (AC)	ChloraPrep [®] - Hi-Lite Orange [®] applicator	36
D	Negative Control (NC)	Sterile 0.9% saline applied with single use applicator	36

3.4 Endpoints

- Primary Endpoints
 - Log CFU/cm² of skin for each treatment per body site per time point.
- Secondary Endpoints
 - Responder rates will be calculated by converting each log₁₀ CFU/cm² reduction at 6 hours post-treatment time point to a binary (yes or no) success measure. Success at 6 hours post-treatment time point is defined as having skin flora counts that are less than or equal to the baseline skin flora counts on both body sites.
- Exploratory Endpoints
 - Log₁₀ CFU/cm² reductions from baseline for each treatment per body site per post-application time point.
 - Product expression volumes: the weight of the treatment applied to a test site will be estimated by subtracting the weight measurement (g) of the treatment after the application from the weight of the treatment (g) before application.
- Safety Endpoints
 - Skin irritation scores (Erythema, Edema, Rash and Dryness scores for each time point)

4 Sample Size

A sufficient number of volunteers will be enrolled in the screening phase such that the total numbers of evaluable samples collected from groin and abdominal regions are not less than 36 evaluable test sites from each treatment arm (minimum of 144 each for groin and abdominal regions). A minimum of 72 evaluable subjects is required to achieve a total of at least 144 test sites for groin and abdominal regions. Subjects must satisfy all Screening Day and Treatment Day Inclusion/Exclusion Criteria prior to screening sample collection and Treatment Day procedures. If the required numbers of subjects do not qualify from the initial screening group, additional volunteers will be recruited.

This is a Phase II study to assess the immediate and persistent antimicrobial effect of the Investigational Products relative to the Negative Control and the Active Control using a log₁₀ reduction study (i.e., average treatment effect) according to the procedures outlined in the Food and Drug Administration Tentative Final Monograph (TFM) for Effectiveness Testing of a Patient Preoperative Skin Preparation (FR 59:116, 17 June 94, pp. 31450-31452) and the test criteria outlined in the deferral letters from the FDA published on January 19, 2017. The purpose is to inform design of future efficacy studies, therefore no sample size calculation was performed to provide statistically-powered evidence of efficacy as part of this study. The sample size is deemed adequate for these purposes.

5 Intended Statistical Software

R 3.2.0 (2015-04-16) or later version if updated.

6 Data

6.1 Data Sets Analyzed

Descriptions of the modified intent to treat (mITT) data, per-protocol data and intent to treat (ITT) data are shown below. Inclusion for the per-protocol data / mITT data set is evaluated for each body area (left and right for the groin and abdomen).

- Modified Intent to Treat (mITT) data: data collected will be included if the treatment-day baseline counts are within the acceptable range ($\geq 3.00 - \leq 5.50 \log_{10} \text{CFU/cm}^2$ on abdominal area, and $\geq 5.00 - \leq 7.50 \log_{10} \text{CFU/cm}^2$ on inguinal area). Data collected will be excluded from mITT data if the treatment-day baseline counts are outside the acceptable range.
 - For responder rate at 6 hours post-treatment time point, missing data at either baseline or a certain time interval will be imputed as non-responders for that time interval in the mITT data.
 - For average treatment effect (ATE) and \log_{10} reduction, missing data will not be imputed for mITT data.
- Per-Protocol data: data collected will be included if the treatment-day baseline counts are within the acceptable range ($\geq 3.00 - \leq 5.50 \log_{10} \text{CFU/cm}^2$ on abdominal area, and $\geq 5.00 - \leq 7.50 \log_{10} \text{CFU/cm}^2$ on inguinal area). Data collected will be excluded from per-protocol data if the treatment-day baseline counts are outside the acceptable range.
 - Missing data at any time interval will not be imputed for ATE, responder rate and log reduction. Missing data will be excluded from per-protocol ATE, responder rate and log reduction analysis.
- Intent to Treat (ITT) data: all randomized subjects with available data will be included and used for the ITT analysis. The full intent to treat (ITT) data set (all randomized subjects) will be used for the safety analysis.

For ATE, responder rate and log reduction, efficacy analyses will be first made on the modified intent to treat (mITT) data set. Efficacy analyses will be also conducted on the per-protocol data set as supportive analyses when per-protocol data are different from mITT data.

For product expression volumes, inclusion of data points will be based on whether the matching data point is included for efficacy for ATE. Analysis will be performed based on the per-protocol data as supportive analyses when per-protocol data are different from mITT data for product expression volumes.

For skin irritation scores, analysis will be performed based on the intent to treat (ITT) data (all randomized subjects).

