## 7.1 Primary Analysis

The primary purpose of the study is to compare the immediate antimicrobial activity of the Investigational Products to the Negative Control and Active Control according to the methods described in the FDA TFM with the statistical analyses outlined in a deferral letter published January 19, 2017. A linear regression model will be used for primary analysis. In the model, the response is the post-treatment  $\log_{10}$  bacterial counts and predictors are the treatment effect and the pre-treatment  $\log_{10}$  bacterial counts as a covariate. The interaction between the treatment and pre-treatment  $\log_{10}$  bacterial counts will also be explored. If there is no significant interaction detected between treatment and pre-treatment  $\log_{10}$  bacterial counts, the interaction term will be removed from the model and the average difference between treatments will be estimated from the linear regression model after correcting for pre-treatment bacterial loads. If there is a significant interaction detected between treatment and pre-treatment  $\log_{10}$  bacterial counts, the average difference between treatments will be estimated from the linear regression model after averaging over the interaction term. The objective is to ensure that the Investigational Products mean treatment effects are non-inferior to the FDA-approved NDA Active Control, within a 0.5  $\log_{10}$  margin for both the abdomen and inguen at 30 seconds and 10 minutes after application; the Investigational Products must have a mean treatment effect of at least 1.2  $\log_{10}$  greater than that for the Negative Control for both the abdomen and inguen at 30 seconds and/or 10 minutes after application. The 95% confidence intervals will be summarized for each product tested, grouped by anatomical site and the post-application time points: 30 second and 10 minute.

Primary analyses will be based on the modified Intent to Treat (mITT) data set with supportive analysis conducted using the Per Protocol data set, as described in Section 15.0. It is expected that the mean treatment effect will meet the standards above, however this is a Phase II study to inform design of future efficacy studies and is not designed to provide statistically powered evidence of efficacy, and the confidence intervals may not lie entirely above the described targets.

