##### Data sets analyzed

The full Intent to Treat (ITT) data set (all randomized subjects) will be used for the safety analysis.

A modified Intent to Treat (mITT) data set will be used for efficacy analyses. Inclusion for the mITT data set is evaluated for each body area (left and right for the inguen and abdomen). For each body area, if the treatment day baseline bacterial count requirements are in the range of 3.00 to 5.50  $\log_{10}/\text{cm}^2$ , inclusive, on the abdomen and 5.00 to 7.50  $\log_{10}/\text{cm}^2$ , inclusive, on the inguen, then the data are included in the mITT data set. Data collected will be excluded from Per Protocol data if the treatment-day baseline counts are outside the acceptable range. Analyses conducted on the mITT data set will also be conducted on the Per Protocol data set as supportive analyses when Per Protocol data are different from mITT data.

- For  $\log_{10}$  CFU/ $\text{cm}^2$  determinations, missing data will not be imputed for either mITT data or Per Protocol data and will be excluded from analysis.
- For responder rate calculations from 6-hour data, missing data will be treated as non-responders in the mITT data, while in the Per Protocol data, missing data will not be imputed and will be excluded from the responder rate Per Protocol analysis.

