7.2 Handling of Missing Data

For mITT responder rate analysis, subjects with missing data at either baseline or a certain time interval will be included as non-responders for that time interval. Responder rate analysis will be performed based on both

per-protocol data and mITT data if there are any missing data identified and if per-protocol data and mITT data are different.

For average treatment effect (ATE), log reduction and product expression volumes, missing data will not be imputed for mITT data. Analysis will be performed based on the per-protocol data as supportive analyses when per-protocol data are different from mITT data.

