7.3 Analysis Methods

For each body site, when per-protocol data are different from mITT data for average treatment effect (ATE), responder rate, log reduction or product expression volumes, per-protocol analysis and mITT analysis will be performed separately using the same statistical methods. The following analysis methods will be applied to both per-protocol analysis and mITT analysis, both abdomen and groin.

An alpha level of 5% (two-sided) is used for all analyses.

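### For the primary treatment-effect analysis, mITT and per-protocol are defined by the same rule, so the supportive per-protocol analysis can never differ from mITT

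*SAP*

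**What the plan says.** SAP 6.1 gives both efficacy sets one inclusion criterion, applied to each body area separately: the baseline taken on the treatment day must lie between 3.00 and 5.50 log10 CFU/cm² on the abdomen, or between 5.00 and 7.50 on the inguen. For mITT: "Data collected will be excluded from mITT data if the treatment-day baseline counts are outside the acceptable range". For per-protocol: "Data collected will be excluded from per-protocol data if the treatment-day baseline counts are outside the acceptable range". Protocol 15.0 states the same limits for mITT and then says: "Data collected will be excluded from Per Protocol data if the treatment-day baseline counts are outside the acceptable range".

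Missing data are also handled alike for the ATE. For mITT, SAP 7.2 says: "For average treatment effect (ATE), log reduction and product expression volumes, missing data will not be imputed for mITT data". For per-protocol, SAP 6.1 says: "Missing data will be excluded from per-protocol ATE, responder rate and log reduction analysis". For product expression, SAP 6.1 says that "inclusion of data points will be based on whether the matching data point is included for efficacy for ATE". The one stated difference is the 6-hour responder rate: a missing value counts as a non-responder in mITT and is left out of per-protocol.

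Protocol 7.1 bases the primary analyses on mITT, "with supportive analysis conducted using the Per Protocol data set, as described in Section 15.0". SAP 7.3 calls for separate analyses "when per-protocol data are different from mITT data for average treatment effect (ATE), responder rate, log reduction or product expression volumes". SAP Table 4 reserves per-protocol ATE columns at each time point, and SAP section 8 plans a list of any subjects who are in mITT but not in per-protocol.

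Protocol 12.0 disqualifies subjects who do not adhere, and Protocol 16.3 requires deviations to be documented. Neither section says whether data then leave an analysis set.

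**The concern.** In a non-inferiority comparison, a per-protocol analysis asks whether the result holds among sites that were treated and sampled as planned. Deviations that make two products look alike pull their difference towards zero, which favours non-inferiority. The 1.2 log10 superiority test against saline answers a different question and does not cover this one.

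Here the set named per-protocol carries no adherence criterion. A site given the wrong product, scrubbed for the wrong time or sampled outside its window stays in both sets if its baseline is in range. The plan provides columns, a trigger and a listing for a difference that its own rules cannot produce for the ATE. At stake is the interpretation of the pass or fail call against the 0.5 log10 margin, which is meant to inform later efficacy studies.

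**Working it through.** **1. Design figures.** SAP 3.3 and section 4 require 36 evaluable sites per arm in each region. 36 × 4 = 144 sites; 144 / 2 sides = 72 subjects; each product appears in 3 pairings of 12 subjects, and 3 × 12 = 36. The plan's figures reproduce.

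**2. The rules side by side for the ATE.**

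| Element | mITT | Per-protocol |
|---|---|---|
| Unit | body area | body area |
| Abdomen baseline | 3.00 to 5.50 | 3.00 to 5.50 |
| Inguen baseline | 5.00 to 7.50 | 5.00 to 7.50 |
| Missing count | not imputed | not imputed, excluded |
| Protocol deviation | no rule | no rule |

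The primary model regresses the post-treatment count on treatment and baseline, so a site without either count cannot enter it. For both sets, then, a site contributes if and only if its baseline is in range and its post-treatment count is observed. Deviation status does not appear in the condition.

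**3. Enumeration.** Four baseline states (in range, low, high, missing) × two post-treatment states (observed, missing) × two deviation states (yes, no) = 16 combinations. ATE membership is the same in both sets in 16 of 16.

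**4. Simulation, as a check on the logic only.** In 500 data sets of 160 sites, with assumed rates of 3% missing baselines and 5% missing post-treatment counts, the ATE sets differed in 0 of 500. The largest difference between regression coefficients was 0.

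**5. Other endpoints.** Log reduction needs the same two counts and has the same missing-data rule, so its sets coincide. Product expression follows ATE inclusion, so its sets coincide too.

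**6. Where the sets can differ.** The one-sided exact 95% lower bound for x responders of n is the 5% quantile of a beta distribution with parameters x and n − x + 1. This reproduces SAP Table 7: 36/36 gives 92.0%, 35/36 gives 87.5%, 34/36 gives 83.5%. Now let one of 36 in-range sites lack its 6-hour count and the rest respond. mITT gives 35/36 = 97.2%, bound 87.5%. Per-protocol gives 35/35 = 100%, bound 91.8%. That difference reflects missing samples, not adherence.

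**7. Precision of a smaller supportive set.** With the same residual SD, interval width is proportional to √(2/n) for n sites per arm. √(36/34) − 1 = 2.9%; √(36/32) − 1 = 6.1%.

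**The case against.** The strongest reply is that the plan already allows for coincidence. Protocol 7.1 refers to Section 15.0, and both Section 15.0 and the SAP run per-protocol only when the data differ. The SAP section 8 listing is likewise conditional. This stands: a reader might infer that a duplicate analysis would be presented as independent confirmation, and the documents do not support that. An ATE per-protocol run would most likely not be triggered. The descriptive statistics in Protocol 7.3 and 15.3 are unconditional for both populations, but those for log reduction would simply repeat.

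Second, other checks exist. Product expression is compared between products (Protocol 15.3, SAP 7.3.3.3), technician may be added to the primary model (SAP 7.3.1), and subjects are questioned about adherence and kept on site (Protocol 13.6). These bear on application and conduct, and they make a high deviation rate speculative. None of them re-estimates the treatment difference without deviating sites. The optional per-protocol analyses in Protocol 7.3 and 15.3 vary the baseline limits, not adherence.

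Third, disqualification under Protocol 12.0 might be meant to remove data. No text says so, or says from which set, so it cannot be relied on to separate the two.

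Fourth, Protocol 13.3 names only low baselines as a reason for leaving mITT, which read alone would let the sets differ at high baselines. Protocol 15.0 and SAP 6.1 both state the upper limits for mITT, so this does not rescue the distinction.

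Fifth, this is a Phase II study that is expressly not powered for efficacy. That limits the consequence, though SAP 7.3.1 still sets formal hypotheses and a success rule.

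**Conclusion.** The point holds for the primary ATE, log reduction and product expression. The per-protocol and mITT sets differ by 0 sites under the written rules, and this depends on no assumed rate or variance. The non-inferiority comparison with the Active Control therefore has no deviation-based sensitivity analysis, despite the statement in Protocol 7.1. It should be corrected, but it does not undermine the primary analysis.

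Three stronger readings are not supported:

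- **That the mITT estimate is biased by this.** It is not; the primary set and model are the same however per-protocol is defined.
- **That a rate of false non-inferiority findings can be attached.** The documents give no deviation rate, the SDs in SAP Table 8 are example values, and any dilution within mITT would be unchanged by redefining per-protocol.
- **That every per-protocol analysis is empty.** The 6-hour responder rate can differ, through its handling of missing values.

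**What to change.** In SAP 6.1 and Protocol 15.0, define per-protocol as mITT sites without a major protocol deviation. Draw the list from requirements the protocol already states: assigned product and side; application and dry time as written in the application instructions; the sampling windows (30 ± 5 seconds, 10 minutes ± 30 seconds, 6 hours ± 30 minutes); and product restriction. Fix both the list and the site-level decisions before plate counts are linked to product information (Protocol 13.9). State whether data from subjects disqualified under Protocol 12.0 stay in mITT. Run the primary model on both sets, with mITT remaining primary.

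Deleting the supportive statement would also make the text consistent, but would leave non-inferiority without this check.

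Costs: a protocol amendment under Protocol 16.2, a SAP revision and one more run of the model, using deviations that are already recorded. The supportive interval would be about 3% wider with 34 sites per arm and about 6% wider with 32. Exclusions made after randomisation can introduce selection, the more so because staff who apply product and collect samples are not blinded, and they disturb the balance of 12 subjects per pairing. The new set should therefore stay supportive only. The primary analysis and the sample size do not change.
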